11.2 Treatment supply and storage

The intravesical gentamicin, intravesical GAGs and oral antibiotics will all be sourced from NHS stocks, as all are considered part of usual standard care processes for the second-line preventative treatment for recurrent UTI.

11.3 Treatment prescribing and dispensing

Treatment will be prescribed and dispensed following local procedures. Gentamicin and GAG should be ordered through inpatient supply route and oral antibiotics should be ordered through outpatient pharmacy. Prescriptions for antibiotics are to be prescribed at randomisation, month 1 and month 3.

11.4 Dosing schedule

Intravesical Prophylactic Treatment:

• Intravesical antibiotics – 80mg of Gentamicin diluted to 50ml using normal saline instilled into the bladder weekly for month 1, fortnightly for Months 2 & 3 and monthly for Months 4,5 & 6*

• Intravesical GAG replacement compounds (laluril, Cystistat, Gepan, etc) – 1 vial of GAG replacement. compound instilled into the bladder weekly for month 1, fortnightly for Months 2 & 3 and monthly for Months 4,5 & 6*

*11 instillations

Comparator:

• Second-line prophylactic daily oral antibiotics as per NICE antimicrobial prescribing guidelines - Nitrofurantoin (50/100mg), Trimethoprim (100mg), Amoxicillin (250mg) or Cefalexin ((125/250mg once a day).

11.5 Dose modification for toxicity

Nitrofurantoin – To discontinue immediately if new or worsening symptoms of pulmonary damage occur.

Trimethoprim is contraindicated in blood dyscrasias, and participants who fit this will be prescribed an alternative antibiotic.

Amoxicillin and cefalexin will not be prescribed to any patient with a history of penicillin hypersensitivity.

Renal function will be determined by eGFR at baseline and if this is less than 45 ml/min nitrofurantoin will not be used

If eGFR is less than 30ml/min the dose of oral trimethoprim will be halved.

Liver function tests will be monitored throughout the trial as some of the antibiotics particularly nitrofurantoin require this.

If alterations in any participants liver function tests in the group randomised to prophylactic antibiotics are identified the local PI will be alerted to this and likely will recommend a change in oral antibiotic agent or re-randomisation to one of the intravesical treatment arms.

11.6 Management of toxicity and hypersensitivity reactions

Follow local policies and procedures as per treating clinician.

11.7 Management of overdose

Follow local policies and procedures as per treating clinician.

11.8 Pre-medication

Not applicable.

11.9 Prohibited medications and interaction with other drugs

All treatments are currently in widespread use in the UK NHS, exhibit a low side-effect profile and have little interaction with other common medications which limits absolute contra-indications to either therapy. Examples of drug interactions are given below:

Trimethoprim – Methotrexate / Clozapine

Amoxicillin – Warfarin / Acenocoumarol

11.10 Permitted concomitant medications

Additional over-the-counter preventive adjuncts such as D-mannose, cranberry supplements and vaginal oestrogen will be permitted in line with current standard clinical care³².

11.11 Trial restrictions

No further restrictions than those already described above.

11.12 Accountability procedures

No medications or associated equipment or consumables are being provided to sites as part of the trial, and therefore, sites are expected to use their own stock. No CTR accountability, recall and disposal procedures are required as described in the VESPER safety Management Plan.

Continuation of the treatments after completion of the 6-month treatment period is not recommended. Following the 6-month treatment period, any additional care, during the 6-month follow up period and beyond is not expected to differ from what is normally expected for patients with recurrent UTIs. It is usual for a period of observation to be undertaken after completion of a period of preventative treatment and the minimum period for this is usually 3 months. Participants will be encouraged to continue without UTI prevention for 6 months following completion of the

intervention but in some cases this may not be possible. If preventative treatment is restarted before the end of the scheduled 6 months post-treatment observation period, then this will be recorded.

11.13 Adherence

Centre for

Canolfan

We will use quantitative data to explore adherence to the allocated intervention and to describe differences between different modes of intravesical administration (self vs clinician-delivered) and the timing of this decision in relation to randomisation and whether this is associated with differential response, switching, and outcomes. We will similarly describe the variability (and association with response/outcomes) in prophylaxis implementation more generally.

12 Sample Management

See Table 1 for schedule of sample collection.

12.1 Urine and perineal sample collection, transport, processing, analysis and storage:

Following usual care procedures, blood samples will be taken from participants to determine renal function (eGFR) at baseline and each follow-up visit. If this is less than 45 ml/min nitrofurantoin will not be prescribed for the oral antibiotic arm. If eGFR is less than 30ml/min the dose of oral trimethoprim will be halved.

Liver function tests will be monitored throughout the trial as some of the antibiotics particularly nitrofurantoin require this.

Mid-stream urine samples for research purposes will be taken at baseline, at all follow-up visits and when participants suspect a UTI based on symptoms and will be sent to the central microbiology laboratory. The central laboratory will determine microbiologically proven UTIs and any antimicrobial resistance (AMR) in all urinary pathogens isolated from urine samples. The samples sent to the central laboratory WILL NOT be used to inform clinical care. Clinical care will be informed by local processes such as the submission of urine samples to the local microbiology services as per current clinical pathways.

We will also assess resistance pattern change in E. coli within the faecal reservoir by obtaining isolates from the optional perineal swabs sent to the central laboratory at baseline, 6 and 12 months.

Canolfan

When participants suspect a UTI based on symptoms at the baseline appointment, a mid-stream urine sample will be sent to the local laboratories by the recruiting site or responsible clinician. During the course of the trial, if a participant suspects a UTI, based on symptoms, they will consult local healthcare services as per usual practice. As part of this a mid-stream urine sample may also be sent to local diagnostic microbiology laboratories (following usual site processes) for identification of microbiologically proven UTIs.

A positive culture will be classified according to UK Health Security Agency (UKHSA) standards for Microbiological Investigations (SMI) B41: Investigation of urine definitions.

Mid-stream urine samples that are being sent to the central laboratory will be collected in appropriately trial labelled sterile 30ml Universal containers containing boric acid. Boric acid will preserve the sample by inhibiting bacterial growth and maintaining the sample's integrity during transport and storage. The urine sample will be transported to the central laboratory in SpeciSafe® transport containers and mailing envelopes which are compliant with UN3373 Regulations for Cat B biological samples.

Urine samples should arrive at the central laboratory as soon as possible.

Perineal swabs (swab with amies transport medium) will be used to collect faecal samples at baseline and at 6 and 12-month follow-up timepoints. Swabs will be returned to the central laboratory in UN3373 regulatory compliant mailing envelopes for Cat B biological samples.

Perineal swabs should arrive at the central laboratory within as soon as possible.

Processing and storage of the urine and perineal samples sent to the central laboratory will be performed according to the VESPER Sample Management and Laboratory Manual.

Processing, analysing and storage of urine and perineal samples will be performed as per section 16.4: Briefly, urine samples will undergo automated microscopy and culture for urinary pathogens according to SMI: B41. Uropathogens will be susceptibility tested using the current standardised EUCAST methods and guidelines.

13 **Trial procedures**

All participants will be enrolled in the trial for 12-months; 6-months intervention period followed by 6-months follow-up period.

The primary clinical outcome will be assessed at the end of the 6-months intervention period and the primary economic outcome will be assessed over the subsequent 6-months follow-up period.

Secondary outcomes will be measured at the end of the 6-months and 12-month periods.

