Follow-up duration Planned trial period Primary objective Secondary objectives Tertiary/Exploratory objectives	12-months post-randomisation (inclusive of 6-months treatment)48 months.The primary objective is to evaluate the clinical and cost-effectiveness of two experimental interventions for women with refractory rUTI: intravesical gentamicin; Intravesical GAG replacement; and compare to the control arm of second-line daily low-dose antibiotic prophylaxis.The secondary objectives are to evaluate the clinical, economic and safety outcomes listed in section 5.4, and to provide a qualitative process evaluation to explore trial processes, intervention mechanisms, and context to inform further implementation.A SMART design will be used and will allow us to explore the optimal sequence of prophylaxis regimens.			
Follow-up durationPlanned trial periodPrimary objectiveSecondary objectivesTertiary/Exploratory objectivesPrimary outcomes	 12-months post-randomisation (inclusive of 6-months treatment) 48 months The primary objective is to evaluate the clinical and cost-effectiveness of two experimental interventions for women with refractory rUTI: intravesical gentamicin; Intravesical GAG replacement; and compare to the control arm of second-line daily low-dose antibiotic prophylaxis. The secondary objectives are to evaluate the clinical, economic and safety outcomes listed in section 5.4, and to provide a qualitative process evaluation to explore trial processes, intervention mechanisms, and context to inform further implementation. A SMART design will be used and will allow us to explore the optimal sequence of prophylaxis regimens. Primary Clinical Outcome 			

	Primary Economic Outcome Incremental cost per quality-adjusted life year (QALY) gained at 12 months.			

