5.3 Primary outcomes measure(s)

The primary clinical effectiveness outcome is the rate of symptomatic, antibiotic-treated UTI, selfreported by participants from randomisation to the 6-month treatment period (verified from medical records).

The primary economic outcome is the incremental cost per quality-adjusted life year (QALY) gained, based on responses to EQ-5D-5L, over 12 months.

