13.1.3 Follow-up assessments

١. 1-month follow-up visit

One month following randomisation the following data and samples will be collected on CRFs. We will allow a time window of 1-month+3 weeks for this follow-up visit.

- rUTI Impact questionnaire
- UTI diary
- EQ-5D-5L
- Adherence to intervention form
- Adverse events
- GP or hospital records checked to confirm any additional urine culture results (outside of the scheduled hospital visits), including resistance patterns of the bacteria cultured
- eGFR & LFT bloods
- Mid-steam urine samples (central lab)

II. 3-months follow-up visit

Three months following randomisation the following data and samples will be collected on CRFs. We will allow a time window of 3-months +4 weeks for this follow-up visit.

- rUTI Impact questionnaire
- UTI diary
- EQ-5D-5L
- Adherence to intervention form
- Adverse events
- GP or hospital records checked to confirm any additional urine culture results (outside of the scheduled hospital visits), including resistance patterns of the bacteria cultured
- eGFR & LFT bloods
- Mid-steam urine samples (central lab)
- III. 6-months follow-up visit

Six months following randomisation the following data and samples will be collected on CRFs. We will allow a time window of 6-months +4 weeks for this follow-up visit.

• rUTI Impact questionnaire

UTI diary

Canolfan

- EQ-5D-5L
- Service use questionnaire
- **Treatment Satisfaction Questionnaire** •
- Adherence to intervention form •
- Adverse events •
- GP or hospital records checked to confirm any additional urine culture results (outside of the • scheduled hospital visits), including resistance patterns of the bacteria cultured
- eGFR & LFT bloods
- Mid-steam urine samples (central lab) •
- Perineal swab (Central lab)

IV. 12-month follow-up visit

Twelve months following randomisation the following data and samples will be collected on CRFs. We will allow a time window of 12-months +4 weeks for this follow-up visit.

- rUTI Impact questionnaire •
- UTI diary •
- EQ-5D-5L •
- Service use questionnaire
- Treatment Satisfaction Questionnaire •
- Adherence to intervention form •
- Adverse events •
- GP or hospital records checked to confirm any additional urine culture results (outside of the • scheduled hospital visits), including resistance patterns of the bacteria cultured
- eGFR & LFT bloods
- Mid-steam urine samples (central lab) •
- Perineal swab (Central lab)
- V. 13-month follow-up

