16.3 Cost effectiveness analysis

The economic analysis will consist of both a within-trial and a model-based economic evaluation. A cost-utility analysis will estimate the incremental cost per QALYs gained at 12 months and over a lifetime horizon. A cost-benefit analysis will estimate the incremental net benefits at 12 months. The

Canolfan

within-trial analysis will be conducted on an intention-to-treat principle. Full details of the health economics analyses will be set out in the Health Economics Analysis Plan (HEAP).

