16.3.2 Outcomes

EQ-5D-5L

The EQ-5D-5L will be administered at baseline, 3-, 6- and 12-months post-randomisation. Responses will be converted into utility values using the UK recommended tariff⁴³. QALYs will be estimated using the area under the curve approach⁴⁴. In a sensitivity analysis the disutility associated with a UTI episode, estimated in a previous NIHR HTA study, will be considered in the QALY calculation³.

Willingness-to-pay to avoid a UTI

Despite considering the disutility associated with a UTI in a sensitivity analysis, given the short duration of UTIs, potential differences in quality of life associated with a reduction in UTIs may not be captured by QALYs. In a previous NIHR HTA study women were asked to value, in monetary terms, how much they would be willing-to-pay to avoid a UTI⁴¹. The average willingness-to-pay value estimated will be inflated to the current price year and combined with the number of UTIs reported by participants in VESPER⁴². This will be presented as the burden of UTIs reported in VESPER on women, in monetary terms, for each of the randomised arms.

Discrete choice experiment

To estimate women's preferences for the trial interventions and their associated outcomes, a discrete choice experiment (DCE) will be administered, to all participants, at month 13, so as to not affect the response rate for other trial outcomes. A DCE involves presenting individuals with a series of hypothetical alternative choice sets, usually pairwise, differing in their attributes and levels, and asking them to indicate their preferred alternative in each set⁴⁵. The key attributes and associated levels reflecting the features and outcomes of the interventions, and a cost attribute will be derived using a literature review, and consultations (likely in the form of interviews and focus groups) with both women and clinicians. Once the attributes and levels have been identified, the DCE will be designed in NGene⁴⁶. The responses to the DCE will be analysed using appropriate regression models, such as conditional logit models and mixed logit models. These regression models will allow us to predict the value and relative importance that participants place on the different attributes of each intervention⁴⁷. The inclusion of a cost attribute will allow us to estimate women's marginal willingness-to-pay for each of the interventions' attributes and the net benefit of the treatments can also be estimated⁴⁸.

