16.3.3 Within-trial analysis

For the within-trial analysis, costs and outcomes will not be discounted as the time horizon is 12months. The economic analysis will compare the interventions in terms of mean costs and effects to estimate cost-effectiveness. Differences in costs and effects will be estimated simultaneously using seemingly unrelated regression, which controls for observed (e.g., age, baseline costs and utilities) and unobserved individual characteristics⁴⁹. If one treatment is not dominant (i.e., less costly and more effective) then, for the cost-utility analysis the incremental cost per QALY gained at 12-months will be estimated; and the cost-benefit analysis will estimate the incremental net benefit.

Sensitivity analysis

To replicate the primary outcome, time horizon, a sensitivity analysis will be undertaken to estimate the incremental cost per QALY gained over the treatment phase (6-months). Only costs and utilities reported between baseline and the 6-month follow-up will be considered in this analysis.

Both deterministic (e.g., variation in unit costs) and stochastic, in the form of the bootstrapping technique, will be used to explore potential uncertainties in costs, effects and cost-effectiveness⁵⁰. This statistical impression will be presented as both cost-effectiveness acceptability curves (CEACs) and cost-effectiveness planes^{51, 52}. For the cost-benefit analysis statistical imprecision will be displayed as cost and willingness-to-pay planes and as the probability of an intervention being efficient (i.e., the probability that the benefit of the intervention is greater than the cost).

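### Section 13 gives the primary economic outcome the wrong window (months 6 to 12 instead of 12 months from randomisation), and the EQ-5D-5L collected at month 1 is missing from the QALY time points

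*Protocol*

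**What the plan says.** **Window.** The opening of Section 13 (Trial procedures) places the primary clinical outcome at the end of the 6-month intervention period and then says that "the primary economic outcome will be assessed over the subsequent 6-months follow-up period". The other places that fix the window read differently:

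- Synopsis, primary outcomes: "Incremental cost per quality-adjusted life year (QALY) gained at 12 months".
- Section 5.3: "The primary economic outcome is the incremental cost per quality-adjusted life year (QALY) gained, based on responses to EQ-5D-5L, over 12 months".
- Section 16.3: "A cost-utility analysis will estimate the incremental cost per QALYs gained at 12 months and over a lifetime horizon".
- Section 16.3.3: "costs and outcomes will not be discounted as the time horizon is 12months".

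The only 6-month economic analysis is a sensitivity analysis of the treatment phase in Section 16.3.3: "Only costs and utilities reported between baseline and the 6-month follow-up will be considered in this analysis". That covers months 0 to 6.

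**EQ-5D-5L time points.** Section 13.1.3 introduces the month-1 visit with "One month following randomisation the following data and samples will be collected on CRFs", and EQ-5D-5L is on the list that follows. Table 1 also marks it at month 1. Section 16.3.2 says "The EQ-5D-5L will be administered at baseline, 3-, 6- and 12-months post-randomisation" and derives QALYs as an area under the curve. Section 5.4 gives the same four points for QALYs. Table 7 gives them for the quality-of-life outcome, which is analysed by linear regression.

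**The concern.** The incremental cost per QALY is one of the trial's two primary outcomes, so its window should read the same throughout. The Section 13 sentence contradicts the definition and matches no planned analysis. A window starting at month 6 would leave out the costs of the initial treatment course and the utilities measured while women are on it.

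The month-1 mismatch concerns an input to the same outcome. Instillations are most frequent early on (weekly in month 1, then fortnightly), so a utility measured near month 1 bears on a period when treatment burden may differ between arms. Section 16.3.2 leaves that measurement out of the administration schedule altogether. The 6-month sensitivity analysis takes utilities reported between baseline and month 6, which read literally would include it. The protocol therefore does not settle whether this measurement enters the QALY.

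**Working it through.** The protocol gives no figure to reproduce here. The check compares the stated windows and then sizes each discrepancy with the trapezoidal area under the utility curve, time in years. The documents give no utility values, so the utility differences below are assumptions shown as ranges.

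**1. What a literal months 6 to 12 window leaves out**

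- Instillations (Section 11.4): weekly in month 1 (4), fortnightly in months 2 and 3 (4), monthly in months 4 to 6 (3). 4 + 4 + 3 = 11, which matches the stated 11. All are scheduled in the 6-month treatment period.
- Time: 6 of 12 months, so 0.5 of the 1.0 year over which QALYs accrue.
- QALY difference: let the between-arm utility difference be 0 at baseline and d at months 3 and 6.
  - If it returns to 0 at month 12, the 12-month difference is 0.125d + 0.25d + 0.25d = 0.625d, of which 0.25d falls in months 6 to 12: 40%. For d = 0.02 that is 0.005 of 0.0125; for d = 0.06, 0.015 of 0.0375.
  - If it stays at d to month 12, the total is 0.125d + 0.25d + 0.5d = 0.875d, of which 0.5d falls in months 6 to 12: 57%. For d = 0.02 that is 0.010 of 0.0175; for d = 0.06, 0.030 of 0.0525.

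**2. What leaving out month 1 does**

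Let u0, u1 and u3 be the between-arm utility differences at baseline, month 1 and month 3.

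- With month 1: (1/12)(u0 + u1)/2 + (2/12)(u1 + u3)/2.
- Without it: (3/12)(u0 + u3)/2.
- Change from adding it: (1/24)(3u1 − 2u0 − u3) = 0.125 × [u1 − (2u0 + u3)/3] = 0.125 × e.

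Here e is the departure of the month-1 between-arm difference from the straight line joining baseline and month 3.

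| Assumed e | Change in between-arm QALY difference |
|---|---|
| 0 | 0 |
| ±0.02 | ±0.0025 |
| ±0.06 | ±0.0075 |

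The omitted area is a triangle with base 3 months and height e. The factor 0.125 therefore does not depend on where between baseline and month 3 the visit falls, provided e is measured from the line at the actual visit date. A deviation common to all arms cancels.

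**The case against.** The strongest reply is that the window is right wherever the outcome is defined or analysed. The synopsis, 5.3, 16.3 and 16.3.3 agree on 12 months. Section 16.3.1 puts intervention costs in the base case and collects service use at baseline, 6 and 12 months. Further detail is left to the Health Economics Analysis Plan. The Section 13 sentence biases the result only if an analyst follows it against all of these. This stands, and it limits the point to a correction of text.

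A reader might infer that the literal window would favour the intravesical arms by removing their cost. The documents do not support that. They give no unit costs, and the same window would also drop on-treatment QALYs, where a benefit of those arms could arise. Nor would months 6 to 12 be free of treatment cost: under Sections 6 and 9.6.2, a woman re-randomised at the end of month 6 receives a further 6 months of treatment inside that window.

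A reader might also infer that the four-point curve is wrong or hides a utility loss from weekly instillation. A curve through baseline, 3, 6 and 12 months is a valid area under the curve, and the loss may be zero. The month-1 visit may take place up to 3 weeks late, and the first instillation is booked after randomisation, so the measurement need not fall in the weekly phase. Removing EQ-5D-5L from the month-1 visit would also end the contradiction. What remains is that the protocol contradicts itself on a measurement it already pays for, and using it replaces an interpolation assumption with data.

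**Conclusion.** Both contradictions are confirmed, and both are minor. Section 13 misstates the window of a primary outcome. If it were followed, half of the QALY year and the treatment-phase costs would be lost, and the window would hold 40% to 57% of the 12-month QALY difference under the two assumed profiles. The direction of the net effect on cost-effectiveness cannot be derived. Leaving out month 1 changes the between-arm QALY difference by 0.125 × e, at most 0.0075 in either direction for an assumed departure of up to 0.06, and by nothing if the difference is linear to month 3.

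It would go too far to say that the planned cost-effectiveness result is distorted. The sections that define and analyse the outcome already specify 12 months, and the four-point calculation is legitimate.

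**What to change.** - Section 13: state that the primary economic outcome is assessed over the 12 months from randomisation.
- Sections 5.4 and 16.3.2 and Table 7: list EQ-5D-5L at baseline, 1, 3, 6 and 12 months. For the QALYs, use all five points in the area under the curve, placed at their actual assessment dates because the visit windows allow late attendance.

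The cost is four wording changes and no new data, since Table 1 and Section 13.1.3 already schedule the month-1 questionnaire. The analysis gains one more time point at which missing values must be handled.
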